# 12.1.8. Additional Efficacy Analyses of the Primary Outcome: Subgroup Analyses (Tertiary Analysis)

The primary efficacy outcome variable is analyzed by the following subgroups, assuming sufficient numbers of subjects are enrolled in the subgroups (~10%):

- Index event type: either TIA or minor stroke
- Age (<65 or≥65)
- Gender
- Race/ethnicity
- Hypertension
- Aspirin use prior to randomization
- Statin use prior to randomization
- Imaging evidence of infarction on initial assessment
- Geographic region of clinical site (US versus all other countries)
- Current Smoker (at time of Index Event) versus former/non-smoker
- Severity of index ischemic stroke among those with index ischemic stroke (baseline NIHSS 0,1 vs. 2,3)
- Risk of index TIA among those with TIA (ABCD2 score >5 vs. <=5)

- Time from index event to randomization (<6 hours, >=6 hours)

\_

• Prevailing aspirin dose (This subgroup analysis will be performed for the primary efficacy and primary safety outcome.)

The treatment effect in each of the subgroups is tested at the two-sided alpha level of 0.05.

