1 STUDY FLOWCHARTS

1.1 Graphical Study Design

1.2 Schedule of Activities and Assessments

Contact Schedule and Measurements

Measurements	Screening	Baseline/ Randomization	Phone F/U Day 7 +/-2	Phone F/U Day 30 ^o	Phone or In- Person F/U Day 90 +/- 14 [†]	Event Visit***	End of Study
Screen Failure Log	x						
Eligibility Form		x					
Consent (including optional study)		x					
Randomization Form		x					
Enrollment/ Demographics		x					
ABCD ² Score		x					
Modified Rankin Scale (mRS)					x	x	
NIH Stroke Scale		x			x	x	x
Medical History		x					
Prior Medications		x					
Index TIA/Minor Stroke Symptoms		x					
Vital Signs		x					
Blood Sample (optional)		x* ²					
Head CT/MRI Scan		x*			x*	x*	
ECG		x*			x*	x*	
Carotid Imaging		x* ¹			x* ¹	x*	
Stroke-Free Questionnaire: QVSFS			x	(x)	x	x	
Morisky Questionnaire			x	(x)	x	x	
Concomitant Medications Form			x		x	x	
SAE/Clinical Outcome Reporting			x		x	x	
Study Drug Compliance				(x)			x
Final Diagnosis		x					
End of Study Form							x
Protocol Violation	x	x	x		x	x	x

*Part of standard evaluation; cost not covered by study.

** As needed (visit can occur more than once).

*** Event Visits for MI can be completed by telephone.

† Preferably as soon as possible after the completion of 90 days.

¹ Encouraged as part of best practices but not required for study entry or at 90 days. If performed, record results on CRF.

² Blood sample obtained with subject's consent for optional ancillary study

Ø No study data collected.

Note: Certain follow-up assessments, such as the mRS and QVSFS, by telemedicine are acceptable.

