2.6 Preliminary Studies

During the past 12 years, a large number of studies that serve as background for this trial have been performed. Many were designed to address issues raised in proposing this trial. These include studies

assessing the prevalence and community knowledge of TIA [127], establishing the high risk of stroke and cardiovascular events after TIA [16, 17, 71], identifying risk factors for stroke and other adverse events [16, 17, 71, 128, 129], defining the importance of early neurological recovery in identifying instability, evaluating current patterns of antithrombotic prescription and other aspects of care after TIA [85, 130-132], identifying predictors of site recruitment in randomized stroke/TIA trials [133], confirming ability to recruit to an acute TIA trial, creating metrics to evaluate the potential impact of clinical trials so that the planned trial can be evaluated in this light [123]. Numerous reviews and editorials have also been written clarifying the urgency of treatment for TIA and the inadequacy of current therapies [98, 134-139]. Due to space constraints, published preliminary work is only reviewed very selectively and briefly.

A series of studies have documented that the risk of stroke is very high in the days to months after a TIA. These results have been confirmed in multiple studies from other institutions, as reviewed in Table 2.1. The first of these studies on this topic was the Emergency Department TIA Study, a cohort study of 1707 patients diagnosed with TIA by emergency physicians at one of 16 hospitals in the Kaiser-Permanente Northern California (KPNC) medical care plan 1997-1998 [16]. Over 90% of patients arrived within 12 hours of symptom onset and 92% received an antithrombotic medication at emergency-department discharge. A total of 180 strokes occurred within 90 days of the index TIA, with an overall 90-day stroke risk of 10.5% (95% CI 9.1% - 12.0%). Hospitalization for myocardial infarction occurred in 1.4% (n=24) during the first 90 days. The 90-day risk of vascular death was 2.3% (n=40), with most deaths attributable to stroke. For the composite outcome of stroke, myocardial infarction, and vascular death, the 90-day risk was 13.0% (n=221). One third of events occurred in the first 24 hours, 50% occurred within the first 5 days, and 73% within the first month.

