4 STUDY DESIGN AND MANAGEMENT OVERVIEW

4.1 Study Design Overview

The primary null hypothesis of this randomized, double-blind multicenter clinical trial is, in patients with TIA or minor ischemic stroke treated with aspirin 50-325 mg/day, there is no difference in the event-free survival at 90 days in those treated with clopidogrel (600 mg loading dose then 75 mg/day)

compared to placebo when subjects are randomized within 12 hours of time last known free of new ischemic symptoms. The primary outcome event is defined as a composite outcome—ischemic stroke, myocardial infarction, or ischemic vascular death.

Patients with high-risk TIA (defined as an ABCD² score ≥ 4) or minor ischemic stroke (defined as an NIHSS ≤ 3), who can be randomized within 12 hours of time last known free from new ischemic symptoms will be enrolled. Subjects will be randomized to receive a clopidogrel 600 mg loading dose then 75 mg/day for the duration of the study, or to receive matching placebo. All subjects will receive aspirin 50-325 mg/day with the dose determined by the treating physician; an aspirin dose of 150-200 mg daily x 5 days, followed by 75-100 mg daily will be strongly recommended. Concomitant use of dipyridamole will be prohibited. Subjects will be followed for 90 days and risks of the composite outcome—ischemic stroke, myocardial infarction, and ischemic vascular death—will be compared in the treatment groups. The trial will be completed in 7 years, with 5,840 subjects recruited from 350 centers in partnership with the NINDS Neurological Emergencies Treatment Trials (NETT) Network and the POINT Clinical Research Collaboration (CRC). Recruitment will occur over 90 months, with a goal rate of 0.40 subjects per site per month for U.S. sites, and 0.47 subjects per site per month for sites outside the U.S., which is based on prior studies of recruitment, on the recruitment rate in the pilot FASTER trial, and on the expectations and past achievements of identified centers. From the perspective of the sites, the trial will be simple. A total of 530 primary outcome events is anticipated.

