6 TREATMENTS

6.1 Study Drugs

This randomized double-blind study is primarily designed to compare a clopidogrel/aspirin combination versus an aspirin alone regimen. The two types of study tablets (75 mg active clopidogrel and placebo) are indistinguishable, identical in size, shape, color, appearance, and taste.

Minor side effects are unusual with the medication [102], so it is not anticipated that either subjects or clinicians will be able to differentiate the placebo from the active drug. Standard laboratory tests cannot detect the effects of clopidogrel.

Investigators will not have access to the randomization (treatment) code, except in exceptional circumstances, such as occurrence of a serious adverse event for which knowledge of the study medication would be considered essential for treating the subject.

Sanofi supplied the blinded study drugs, clopidogrel 75mg and matching placebo, distributed by the UCSF Drug Product Service Laboratory (DPSL) for US sites and Pharmacy Services partners for OUS sites

in quantities sufficient to last through May 2016. From June 2016 forward, additional supplies of blinded study drug (clopidogrel and matched placebo) after that date will be provided by Sharp Clinical Services, Inc. in quantities sufficient to last through the end of enrollment.

Aspirin tablets will be open label with the dose in a range 50-325 mg daily determined by the treating physician. A dose of 150-200 mg daily x 5 days, followed by 75-100 mg daily will be strongly recommended.

The clopidogrel/aspirin group will receive the following treatment:

- Day 1*: 8 tablets of clopidogrel 75 mg (loading dose of 600 mg)
- From D2 to D90: one tablet of clopidogrel 75 mg and 50-325 mg of aspirin per day

The placebo/aspirin group will receive the following treatment:

- Day 1*: 8 tablets of placebo 75 mg (loading dose of 600 mg)
- From D2 to D90: one tablet of placebo 75 mg and 50-325 mg of aspirin per day

*Subjects will receive open label aspirin (50 mg – 325 mg), with dose at the discretion of the treating physician.

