# 12.1.6. Additional Efficacy Analyses of the Primary Outcome: Adjusting for Covariates (Tertiary Analysis)

For other exploratory analyses of the primary outcome variable, the composite event is assessed for treatment differences adjusting for a variety of covariates deemed clinically or prognostically important, such as age and time between symptom onset and randomization, whether a brain infarction is demonstrated on an initial scan. These adjustments are made in the form of a Cox proportional hazards model. Each covariate is evaluated individually first with a model that includes an interaction effect with the treatment (clopidogrel or placebo). If a significant interaction (p<0.10) is observed, subgroup analyses may be considered (see Section 12.1.7). Quantitative and qualitative interaction between the treatment and each covariate also are visually assessed by graphical methods. A multivariable model that includes covariates that contributed significantly (p<0.05) as treatment modifiers individually may then be constructed.

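### SAP 12.1.8 judges subgroups by separate within-group tests at 0.05, and leaves the aspirin-dose group without a time anchor, cut-point or source

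*SAP*

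**What the plan says.** SAP 12.1.8 lists 14 subgroups for the primary efficacy outcome. The last is "Prevailing aspirin dose (This subgroup analysis will be performed for the primary efficacy and primary safety outcome". It is the only one expressly extended to the safety outcome. The section's only statement on testing is: "The treatment effect in each of the subgroups is tested at the two-sided alpha level of 0.05".

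Many neighbouring items carry a cut-point (age 65, NIHSS 0,1 versus 2,3, ABCD2 5, 6 hours) or a baseline anchor, such as "Aspirin use prior to randomization". The dose item has no cut-point, time point, rule for dose changes or source form.

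SAP 12.1.6 describes a Cox model for covariates: "Each covariate is evaluated individually first with a model that includes an interaction effect with the treatment (clopidogrel or placebo". An interaction with p<0.10 may lead to subgroup analyses. Its examples are age, onset-to-randomization time and infarction on the initial scan; aspirin dose is not named. It points to 12.1.7. The SAP contents list shows 12.1.7 as the subgroup section, but in the body 12.1.7 is the on-treatment analysis and subgroups are 12.1.8.

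On aspirin itself, Protocol 6.1 says "Aspirin tablets will be open label with the dose in a range 50-325 mg daily determined by the treating physician", and Protocol 4.1 adds that "an aspirin dose of 150-200 mg daily x 5 days, followed by 75-100 mg daily will be strongly recommended". In the emergency-department cohort of Protocol 2.6, "One third of events occurred in the first 24 hours, 50% occurred within the first 5 days, and 73% within the first month". The schedule in Protocol 1.2 marks the "Concomitant Medications Form" at Day 7, Day 90 and event visits, with no mark at baseline.

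**The concern.** There are two separate issues.

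**The test.** A significant result in one group and a non-significant one in the other does not show that the effects differ. With unequal groups it is the expected pattern when the effects are the same. Read literally, 12.1.8 invites the conclusion that clopidogrel works at one aspirin dose and not at the other. This applies to every subgroup listed.

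**The grouping.** Prior aspirin use is already its own subgroup, so *prevailing* dose most naturally means the open-label dose taken on study. That is a post-randomization value, and the recommended regimen changes it after day 5. If an analyst coded the dose at the event, or the commonest dose up to it, a patient who would have stepped down but had an early event would count as higher-dose because of that event.

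**Working it through.** **1. The plan's own power.** For d events and 1:1 allocation, power ≈ Φ(|ln HR|·√d/2 − 1.96). SAP 5.1 gives HR 0.75 and 530 events: 0.2877 × 23.02/2 = 3.31, and Φ(1.35) = 0.91, against a stated 90%. The formula fits the design.

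**2. Unequal groups, same effect.**
- Placebo risk at 5,840 patients: 4,150 × 0.1524/5,840 = 10.83%, assuming the re-estimation kept the expected event count.
- Active risk at HR 0.75: 1 − (1 − 0.1083)^0.75 = 8.24%.
- Events: 2,920 × (0.1083 + 0.0824) = 557.
- Assumed dose mix (not in the documents): 70% step down, 15% stay higher, 15% are lower throughout. Grouped by day-1 dose this is 85:15, or 473 and 84 events.
- Larger group: 0.2877 × √473/2 = 3.13, power 0.88. Smaller group: 0.2877 × √84/2 = 1.32, power 0.26.
- Significant in the larger group only: 0.879 × (1 − 0.261) = **0.65**.

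Simulation (2,000 trials per setting) gave 66% for this mix, 51% at 50% step-down and 39% at 30%. The interaction test rejected in about 5-6%.

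**3. Equal halves.** With 265 events each: 0.2877 × √265/2 = 2.34, power 0.65. Exactly one significant: 2 × 0.649 × 0.351 = **0.46**.

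**4. Power of the interaction test.** Using RRR 23% directly gives 2,920 × 0.1083 × 1.77 = 560 events, split 476 and 84. The standard error of the difference in log HR is √(4/476 + 4/84) = 0.237. For 80% power the ratio of HRs must be exp(2.80 × 0.237) = **1.94**, or 0.52 in the other direction.

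**5. Event rates if the group depends on the event.** Event timing is interpolated linearly from Protocol 2.6: 50% by day 5, and 0.50 + 0.23 × 5/25 = 54.6% by day 10. That cohort is timed from the index TIA; using it from randomization is an assumption. Let f be the share of step-down patients' events that are coded higher-dose. There is no true dose effect. Placebo rate in the higher group = 0.1083 × (0.15 + 0.70f) / (0.15 + 0.70 × 0.1083 × f).
- Commonest dose up to the event, f = 0.546: 0.0576/0.1914 = 30%, against 0.0507/0.8086 = 6% in the lower group.
- Dose at the event, f = 0.50: 0.0541/0.1879 = 29%, against 0.0541/0.8121 = 7%.
- Predominant dose over 90 days, where only fatal early events are cut short, f = 0.546 × 40/221 = 0.099: 0.0237/0.1575 = 15%, against 0.0846/0.8425 = 10%.

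At 30% step-down the first comparison falls to 15% versus 8%.

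**6. Treatment comparison under the same sorting.** False treatment-by-dose rejections at 0.05, no true dose effect, 70% step-down, 1,500 simulated trials per setting (simulation error about 0.6 points at 5%, 1.3 at 45%):

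| HR over time | Dose up to event | Dose at event |
|---|---|---|
| 0.75 constant (design) | 5% | 5% |
| 0.67 to day 30, then 1.0 | 13% | 13% |
| 0.60 to day 5, then 0.90 | 25% | 30% |
| 0.60 to day 10, then 1.0 (upper end) | 45% | 42% |

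Predominant dose over 90 days gives 4-7% and day-1 dose 4-6% in all shapes tried. At 30% step-down the first column becomes 6%, 7%, 10% and 14%. If every patient steps down, the higher-dose group under the at-event coding contains only patients with an event, and its HR is about 1.0 whatever the drug does.

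**The case against.** A reader might infer that the aspirin-dose analysis will sort early events into the higher-dose group and produce a false treatment-by-dose interaction. The documents do not support that. The SAP does not say that dose is taken at or up to the event. Predominant dose over the whole study is an equally natural reading, and follow-up continues to day 90 after an event (Protocol 9.4.3). At the design HR of 0.75 there is no false interaction under either event-dependent coding. Every inflated figure in step 6 needs both an assumed step-down share and an assumed change of effect over time, and the documents give neither. Event visits may also coincide with the 90-day visit, after the step-down, which weakens the sorting. The 30% versus 6% contrast is between dose groups, and 12.1.8 does not test it.

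A reader might also infer that the SAP has no interaction test. It has one in 12.1.6, with an open covariate list and a link to subgroup analyses through an outdated section number.

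What stands: 12.1.8 itself names only within-group tests and lists its subgroups without waiting for the 12.1.6 step. No text ties that model to aspirin dose. The dose group is undefined. A changing effect is not far-fetched, since Protocol 2.4 suggests that benefit may be greatest early and SAP 12.5.1 plans analyses by time period.

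**Conclusion.** The concern holds in two limited parts.

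- **Testing.** This part does not depend on how dose is defined. With one common HR of 0.75, separate tests disagree in about 46% of trials for equal halves, and favour the larger group alone in about 65% at the assumed 473:84 split. The split is an assumption; the direction of the problem is not.
- **Definition.** The dose group needs a time anchor, cut-point and source. Event-dependent coding would distort event rates by dose group. It would distort the treatment comparison only with a time-varying effect or near-universal step-down.

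If major hemorrhage is spread evenly over follow-up, at 1% versus 2% (expected rate in SAP 13.2, excess in Protocol 8.1), the safety treatment ratio stays about 2.0 in both dose groups. The documents give no timing for bleeds. The analysis is tertiary, the primary result is unaffected, and the severity is minor.

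**What to change.** Before unblinding:

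1. For aspirin dose and the other 12.1.8 subgroups, base the conclusion on the treatment-by-subgroup interaction from the 12.1.6 Cox model. Report each group's HR with its 95% CI instead of relying on separate 0.05 tests. Correct the 12.1.6 pointer to 12.1.8.
2. State that the aspirin-dose group must not be set by the dose at, or truncated at, an outcome event. Use the day-1 dose if it was recorded. Otherwise use the predominant dose over the full 90 days, or a Day 7 landmark that counts only later events, labelled as a non-randomized grouping. State the cut-point and source form.

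The cost is SAP wording, one derived variable and a check on whether a day-1 dose exists, since the schedule marks no such record. The downsides are:

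- The interaction test has low power: a ratio of HRs of about 1.9 is needed for 80%.
- The day-1 lower-dose group is 15% of patients in this illustration, 10% at 80% step-down and 5% at 90%, against the section's floor of about 10%.
- Full-period dose keeps some imbalance in event risk (15% versus 10% above).
- A Day 7 landmark drops about half of the events.

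No aspirin dose is proposed.

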### 12.2. Interim Efficacy Analysis

For the interim analyses of the composite event for the primary efficacy analysis, O'Brien and Fleming (1979) stopping boundaries are adopted. Assuming that the two interim analyses occur after approximately 177 (1/3 of 530 total events) and 353 (2/3) events have been observed and adjudicated, the nominal alpha levels to reject the null hypotheses for overwhelming efficacy are as follows:

POINT Trial Statistical Analysis Plan (Version 8: Sept 2017)

Table 2. Nominal Critical values and Alpha Levels for Three Interim Analysis for Overwhelming Efficacy (O'Brien-Fleming,  $\alpha$ =0.05 two-sided)

| Analysis Order | Number of Events | Nominal critical point (Z-value scale) | Alpha level |
|----------------|------------------|--|-------------|
| 1              | 177              | ±3.710                                 | 0.0002      |
| 2              | 353              | ±2.511                                 | 0.012       |
| Final          | 530              | ±1.993                                 | 0.0463      |

Depending upon the DSMB request, additional interim analyses may be conducted. The spending function approach gives flexibility in the timing and frequency of interim analyses. The most current version of the EAST® software (Cytel Corporation) is used as the interim monitoring tool.

At any interim analysis, if we cross the stopping boundary, the DSMB may recommend stopping the study for overwhelming efficacy of one treatment over the other, although the better treatment may not necessarily be clopidogrel. If and only if the stopping boundary is crossed, prior to making the final decision for recommendation to stop the study, it is expected that the DSMB would request thorough analyses of secondary outcomes and subgroup analyses to confirm the findings of the primary outcome results.

### 12.3. Interim Futility Analysis

Futility analyses are planned to be conducted to coincide in timing with the tentatively scheduled interim analyses for efficacy (at three equal intervals of information). However, if the recruitment is much slower than anticipated or if new information from sources external to the study about the clopidogrel treatment becomes available, the futility of the therapy may be assessed earlier or in between planned intervals of interim analyses.

The stochastic curtailment method is adopted based on conditional power (Lan KKG et al, 1982). The informal criterion for determination of futility is that at each interim look, if the conditional power (defined as the probability of rejecting the null hypothesis at the final analysis given the data accumulated so far and under the assumption that the alternative hypothesis under the original design is true) falls below 20%, then the DSMB evaluates all study information (such as overall recruitment rate and secondary outcome assessment data) to consider stopping the study for futility. The evaluation is conducted in a blinded manner.

[figure not shown]
Evaluation of futility using conditional power allows flexibility in that it can be calculated and assessed at anytime during the study without inflation of the Type I error probability and that the threshold does not necessarily have to be pre-specified. The drawback is that the overall Type II error probability may not be preserved, whereas a formal but less flexible hypothesis testing approach using the beta-spending function for futility boundaries (Pampallona S et al, 2001) does preserve power. However, for the POINT Trial, the flexibility

of this informal approach to assessing futility holds more appeal because it allows other information to be taken into consideration, such as recruitment and safety data and conditional power at other alternative effect sizes (Freidlin B and Korn EL, 2002).

An interim monitoring tool, the most current version of the  $\mathsf{EAST}^{\circ}$  software is used to estimate the conditional power.

POINT Trial Statistical Analysis Plan (Version 8: Sept 2017)

### 12.4. Interim Monitoring Schematic

### 12.5. Secondary and Tertiary Clinical Efficacy Outcomes Analyses

### 12.5.1. Secondary Analyses

Several secondary analyses will be performed to evaluate of the impact of therapy. Prior to these analyses, univariate analyses of covariates, identified from previous studies as having confounding effect on the outcome measurements, are conducted to determine their inclusion in the multivariable models. In addition, stepwise regression methods may be applied to assess the best set of covariates to include in a particular model. Some of the suspected significant confounders are: age, time from symptom onset to randomization, African Americans, those previously taking aspirin, those with index TIA vs. minor ischemic stroke.

The usual verification of variable and model assumptions and goodness of fit assessments accompany each analysis. Time to event outcomes will be assessed via log rank test (unadjusted) and via cox proportional hazard model adjusting for covariates. A Wilcoxon log-rank test will be used for ordinal outcomes (mRS). A logistic regression will be used for binary outcomes (90 day mRS). The significance of each test is set at a two-sided alpha of 0.05.

ITT analyses and As-treated analyses will be performed for the following secondary outcomes for efficacy/net-benefit:

- Composite event of ischemic stroke, MI, ischemic vascular death, or major hemorrhage
- Ischemic stroke
- Ischemic vascular death
- MI
- Composite event of ischemic stroke and hemorrhagic stroke

ITT analyses and As-treated analyses for efficacy/net-benefit will be performed for the following secondary outcomes for safety/tolerability:

- Primary efficacy outcome from day 0 to 7 and day 8 to 90, and from day 0 to 30 and day 31 to 90 (HR and 95% CI will be calcuated via cox model for each time point stratified)
- Primary safety outcome from day 0 to 7 and day 8 to 90, and from day 0 to 30 and day 31 to 90 (HR and 95% CI will be calcuated via cox model for each time point stratified)
- All-cause Death
- Hemorrhagic stroke
- Symptomatic intracerebral hemorrhage
- Other symptomatic intracranial hemorrhage (SAH, SDH or IVH)
- Major Hemorrhage other than Intracranial Hemorrhage
- All minor hemorrhage (including asymptomatic intracranial hemorrhage)

